### **8.4.3 Withdrawal and Replacement of Subjects**

#### **8.4.3.1 Criteria for Subject Withdrawal**

In accordance with the Declaration of Helsinki ([Appendix 1 \[Section 17.1\]](#)) and other applicable regulations, a subject has the right to withdraw from the study at any time and for any reason without prejudice to his or her future medical care by the physician or at the institution.

Subjects may also be withdrawn from the study for any of the following reasons:

- The Investigator decides that the subject should be withdrawn. If this decision is made because of an intolerable adverse event or a clinically significant laboratory abnormality, the study medication is to be discontinued and appropriate treatment is to be provided. The Sponsor or designee is to be notified immediately.
- The subject requires a change in the type or brand of insulin (other than a change in dosage)
- The subject is unwilling to continue in the study
- Lack of compliance with protocol
- The Investigator or the Sponsor stops the study per [Section 15.8](#)
- The subject fails to respond to the study medication at an acceptable level, and the subject or Investigator determine another treatment is preferable.
- The subject fails to return to the clinic for scheduled visits and does not respond to telephone calls or written attempts at communication.

- If a subject becomes pregnant during the study, she will discontinue IP immediately, report the pregnancy to the Investigator, and attend an end-of-treatment visit. If the female partner of a male subject becomes pregnant, the subject may continue in the study but the pregnancy should be reported. See [Section 11.7](#) of this document for more details about pregnancy reporting procedures.

The reason for withdrawal will be recorded in the clinical records and the electronic Case Report Form (eCRF). All subjects who are withdrawn from the study will attend an end-of-treatment clinic visit (see [Section 9.10](#)). All subjects who are withdrawn from the study should be offered appropriate follow-up medical care.

#### **8.4.3.2 Replacement of Subjects**

Subjects who withdraw from the study will not be replaced.

### **8.5 Treatment**

#### **8.5.1 Treatments Administered**

Subjects will be randomized to receive either Lantus® or Gan & Lee Insulin Glargine Injection for subcutaneous injection. Details of each product are shown in [Table 2](#).

**Table 2: Identity of the Investigational Medicinal Products**

Drug Name	Gan & Lee Insulin Glargine Injection	Lantus®
Manufacturer	Gan & Lee Pharmaceuticals, China	Sanofi-Aventis Deutschland GmbH, Germany
Formulation	Solution	Solution
Strength	100 U/mL	100 U/mL
Route of administration	Subcutaneous	Subcutaneous

Lantus® contains insulin glargine, an insulin analog, and has a prolonged duration of action. Lantus® and Gan & Lee Insulin Glargine should be administered once daily at any time but at the same time each day. To be consistent with current Lantus® labeling, twice-daily dosing of IP is strictly prohibited. The dose regimen (dose and timing) should be individually adjusted. In patients with type 2 diabetes mellitus, Lantus® and Gan & Lee Insulin Glargine Injection can also be given together with OAMs.

Gan & Lee Insulin Glargine will be contained in Gan & Lee injector pens (3.0-mL pre-filled glass cartridge) for multiple dose administration.

Lantus® will be provided in 3.0-mL SoloStar® pre-filled pens.

Subjects will follow instructions provided by the Investigator and/or designee regarding proper dose administration of IP and use of the insulin pens, glucometer and related supplies, and the frequency of glucose testing.

## 8.5.2 Study Treatment Formulation

### 8.5.2.1 Gan & Lee Insulin Glargine Injection

The experimental drug is Gan & Lee Insulin Glargine Injection manufactured by Gan & Lee Pharmaceuticals (Beijing, China). This formulation is a clear, colorless, sterile solution for subcutaneous injection, and the concentration is 100 U/mL.

### 8.5.2.2 Lantus®

The active comparator, Lantus® (insulin glargine injection) solution for subcutaneous injection, is a basal insulin analog manufactured by Sanofi-Aventis. This formulation is a clear, colorless, sterile solution, and the concentration is 100 U/mL.

## 8.5.3 Dose and Administration of the Investigational Product

The dosage of IP should be determined by the physician, according to the requirement of the subject. Insulin glargine preparations should be given by subcutaneous injection only.

Subcutaneous administration should be in the upper arms, thighs, buttocks, or abdomen. Use of injection sites should be rotated according to clinical practice.

When administered subcutaneously, care should be taken when injecting insulin glargine to ensure that a blood vessel has not been entered. After injection, the site of injection should not be massaged.

#### **8.5.4 Study Treatment Labeling and Packaging**

Both Gan & Lee Insulin Glargine Injection and Lantus® will be supplied and appropriately labeled in accordance with all national and local regulatory requirements.

#### **8.5.5 Blinding of Study Medication**

Not applicable to this open-label study

#### **8.5.6 Study Treatment Storage and Accountability**

##### **8.5.6.1 Study Treatment Storage**

Investigational product must be kept in an appropriate, limited-access, secure location. The storage area should be labeled “For Investigational Use.” The Investigator or designee must maintain a log of temperature for the refrigerator in which IP is stored and must record and evaluate the temperature of the storage site in accordance with all applicable standards.

##### **8.5.6.1.1 Gan & Lee Insulin Glargine Injection**

Before opening, store Gan & Lee Insulin Glargine Injection in a refrigerator at 36 to 46° F (2 to 8°C). Do not freeze or place next to the freezer or a freezer pack. Keep the unopened Gan & Lee Insulin Glargine Injection pens in the outer carton to protect from light. After its first use, the pen must be stored not above 30°C (86°F), for a maximum of 4 weeks. Do not refrigerate. Keep the pen protected from light.

##### **8.5.6.1.2 Lantus®**

Lantus® should not be stored in the freezer and should not be allowed to freeze. Discard Lantus® if it has been frozen. Protect Lantus® from direct heat and light. Unopened Lantus® that is not in use should be stored refrigerated at 36° to 46°F (2° to 8°C). After a Lantus® SoloStar® insulin pen is opened and in use, it should be stored at room temperature below 86°F (30°C) for a maximum of 28 days. Once opened, the Lantus® SoloStar® pen should not be refrigerated.

##### **8.5.6.2 Study Treatment Accountability**

The Investigator is required to document the receipt, issue, and return or destruction of IP provided by the Sponsor, in accordance with GCP.

No IP may be dispensed to any person not enrolled in the study. The Investigator or designee will count and reconcile drug supplies at the site before either returning them to Gan & Lee Pharmaceuticals or designee at the end of the study.

### 8.5.7 Gan & Lee Insulin Glargine Injection Pen and the Lantus® SoloStar®

The Gan & Lee Insulin Glargine Injection pen and the Lantus® SoloStar® are disposable, multiple-dose, “dial and push”-type variable dose pens intended for the subcutaneous administration of insulin. The injector pen and the drug product (in a 3.0-mL pre-filled glass cartridge) form a single integral product and will be used in conjunction with needles in a suitable range of sizes to be determined by the Investigator’s team. The 3-mL pre-filled glass cartridge contains 300 units of insulin and a maximum deliverable dose of 1 to 80 units with a dose increment of 1 unit. The Investigator or designee will train subjects regarding proper use and handling of the insulin pens for the study and instruct subjects to bring used insulin kits to clinic visits when all the pens needed in a kit have been used. At the end-of-treatment visit, subjects will bring all used and unused kits to the clinic.

### 8.5.8 Dose Adjustments and Dose Escalation

#### 8.5.8.1 Subjects Already on Basal Insulin

During the 2 weeks between screening and randomization, subjects will have their insulin dosing optimized according to [Table 3](#). They will also have any appropriate adjustments in their OAM therapy that may be required because of the optimization of their insulin dosing.

#### 8.5.8.2 Subjects Not Currently on Basal Insulin Therapy

##### 8.5.8.2.1 Pre-Randomization

During the 2 weeks between screening and randomization, subjects will have their OAM dosing optimized to prepare them for starting basal insulin therapy.

##### 8.5.8.2.2 Post-Randomization Insulin and OAM Optimization

Subjects will be prescribed a dose of Lantus® or Gan & Lee Insulin Glargine Injection that will be individually adjusted according to the metabolic status of the subject and at the discretion of the clinical investigational team at the site. During the 4 weeks following randomization, these subjects will have their insulin dosing optimized according to [Table 3](#). They will also have any appropriate adjustments in their OAMs that may be required because of the optimization of their insulin dosing. Optimizing the dose before the randomization visit will reduce the need for dose adjustments during the study. Subjects will follow the instructions provided by the Investigator regarding any dose adjustments and other details regarding the clinical management of glucose and insulin.

**Table 3: Basal Insulin Dose Adjustment Based on Fasting Glucose Result**

Lowest Average Fasting Plasma Glucose (Pre-Breakfast) Value for 3 Days	Adjust Basal Insulin Dose (Units per Dose)
> 271 mg/dL (> 15.1 mmol/L)	+ 6 U
181 – 270 mg/dL (10.1 – 15.0 mmol/L)	+ 4 U
151 – 180 mg/dL (8.4 – 10.0 mmol/L)	+ 2 U

Lowest Average Fasting Plasma Glucose (Pre-Breakfast) Value for 3 Days	Adjust Basal Insulin Dose (Units per Dose)
131 – 150 mg/dL (7.3 – 8.3 mmol/L)	+ 1 U
71 – 130 mg/dL (> 3.9 – 7.2 mmol/L) (Target Level)	Maintain Current Dose
56 – 70 mg/dL (3.1 – 3.9 mmol/L)	- 2 U
< 56 mg/dL (< 3.1 mmol/L)	- 4 U

### 8.5.8.3 Hypoglycemia

The time of occurrence of hypoglycemia may change with a change of insulin regimen, depending on the action profile of the insulins used. Because Lantus® has a more sustained basal insulin supply, fewer nocturnal but more frequent early morning episodes of hypoglycemia can be expected. Particular caution should be exercised, and intensified blood glucose monitoring is advisable for subjects in whom hypoglycemic episodes might be of particular clinical relevance, such as subjects with significant stenoses of the coronary arteries or of the blood vessels supplying the brain (risk of cardiac or cerebral complications of hypoglycemia), and for subjects with proliferative retinopathy, particularly if they have not been treated with photocoagulation (risk of transient amaurosis following hypoglycemia).

Subject adherence to the prescribed medication, diet, and exercise regimens; correct insulin administration; and awareness of symptoms are essential to reduce the risk of hypoglycemia. The prolonged effect of subcutaneous insulin glargine may delay recovery from hypoglycemia. If normal or decreased HbA1c values are noted, the Investigator should consider the possibility of recurrent, unrecognized (especially nocturnal) episodes of hypoglycemia.

Investigators will advise each subject about circumstances in which warning symptoms of hypoglycemia may be different, diminished, or absent, and that hypoglycemia (and possible loss of consciousness) may occur before the subject is aware of any symptoms.

Some factors that may increase the susceptibility to hypoglycemia and require particularly close monitoring and possible dose adjustment include:

- Markedly improved glycemic control after starting the study treatment
- A known tendency to gradually develop hypoglycemia
- Older subject age
- Switching from animal insulin to human insulin
- Autonomic neuropathy
- A long history of diabetes
- Psychiatric illness
- A change in the site of injection from one body area to another
- Conditions that may improve insulin sensitivity such as decreased stress
- Unusual, increased, or prolonged physical activity

- Intercurrent illness such as vomiting or diarrhea
- Inadequate intake of food and/or liquids
- Missed meals
- Alcohol consumption
- Uncompensated endocrine disorders such as hypothyroidism, anterior pituitary or adrenocortical insufficiency
- Concomitant medications that may enhance the blood glucose-lowering effect and increase susceptibility to hypoglycemia, such as angiotensin converting-enzyme inhibitors, disopyramide, fibrates, fluoxetine, monoamine oxidase inhibitors, pentoxifylline, propoxyphene, salicylates, and sulfonamide antibiotics
- Concomitant medications that block the sympathetic nervous system such as beta-blockers

### **8.5.9 Previous and Concomitant Therapy**

Administration of concomitant medications must be reported in the appropriate section of the eCRF, with dosage information, dates of administration, and indication for use. Investigators and site staff should use generic names for concomitant medications if possible. All fields should be completed on the eCRF. See [Appendix 3 \(Section 17.3\)](#) for a list of allowed and prohibited concomitant medications.

### **8.5.10 Treatment Compliance**

Investigators and site staff will review each subject's treatment medication use at scheduled clinic visits and telephone calls, and at any interim clinic visits, and study treatment compliance will be assessed.

### **8.5.11 Assignment to Treatment**

Randomization will be performed through IXRS. The Investigator or designee will access the IXRS to randomize enrolled subjects. The IXRS system will assign a unique randomization number and study medication kit number. No subject may be randomized more than once, and no randomization number will be assigned to more than 1 subject.

### **8.5.12 Unblinding Procedures**

Not applicable for this open-label study.

## **8.6 Study-Related Devices**

### **8.6.1 Glucometer, Test Strips, and Related Supplies**

At the screening visit, each subject will be issued with a glucometer, test strips, and other supplies for use during the study to document hypoglycemic episodes in a prospective manner. The Investigator or qualified site staff will train each subject on the correct use of these supplies and any related procedures, and subjects can obtain additional supplies as

needed at subsequent study visits. Subjects will also be issued a Hypoglycemic Events Record in which they will fully record information prospectively about any hypoglycemic events. They will bring this record to each study visit except those brief visits for application of a CGM sensor. Subjects will be allowed to keep the glucometer after the study per local, ethical and legal guidelines and regulations.

### **8.6.2 FreeStyle Libre Pro Flash Glucose Monitoring System**

The FreeStyle Libre Pro Flash Glucose Monitoring System is a glucose-monitoring device indicated for detecting trends and tracking patterns in persons (age 18 and older) with diabetes.

The FreeStyle Libre Pro Flash Glucose Monitoring System aids in understanding the person's glucose profile and detecting episodes of hyperglycemia and hypoglycemia.

Interpretation of the FreeStyle Libre Pro Flash Glucose Monitoring System readings will be based on the trends and patterns analyzed through time using the reports available.

The FreeStyle Libre Pro Flash Glucose Monitoring System consists of a sensor with an applicator, and reader that is used to start the sensor on the subject and gather the glucose data at the end of the CGM period. The sensor has a small, flexible filament that is inserted just under the skin. The sensor can be worn for up to 14 days. Multiple subjects can have their sensor started by the same reader. Once applied, a sensor will measure and store the glucose readings every 15 minutes. Each site will have a single reader that will be used for all their subjects. Readings from the FreeStyle Libre Pro Flash Glucose Monitoring System will not be made available to subjects in real time and so they will continue performing glucose self-testing with the glucometer according to the Investigator's instructions. The FreeStyle Libre Pro Flash Glucose Monitoring System will be used for data collection purposes only and will not be used to make treatment decisions. The system does not require any subject action.

At the screening visit and between 8 and 10 days before the visits at Weeks 12 and 26, subjects will attend a brief visit so the Investigator or designee can apply a CGM sensor to the back of the upper arm according to the instructions in the FreeStyle Libre Pro User Guide. Subjects will also receive a Mealtime & Insulin Dose Record in which they will record the time of meals and insulin doses for the 8-day CGM period.

Eight days after the screening visit, the subject may remove the sensor and will bring it to the randomization visit in a provided biohazard bag; if the end of the 8-day CGM period coincides with the date of the randomization visit, the sensor can be removed at the visit by site staff. Subjects will bring both their Hypoglycemic Events Record and their Mealtime & Insulin Dose Record to the randomization visit.

For the visits at Weeks 12 and 26, the subject will have worn the sensor for the 8-day CGM period before the visit, and the site staff will remove the sensor at the visit. The Investigator

or designee will use the reader to retrieve the data from the sensor, and the 8-day Mealtime & Insulin Dose Record will be collected and reviewed. The data from the sensor does not need to be uploaded at the time of the visit, but the Investigator will retain each subject's sensor until it is confirmed the data have been successfully uploaded. Each sensor will be labeled with the subject and visit number and will be stored in a secure location until the end of the study after confirmation of successful upload.

Investigators and staff will review the FreeStyle Libre Pro Flash Glucose Monitoring System warnings and limitations and instruct subjects about the need to avoid medications and conditions that could interfere with the results.

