## **8. INVESTIGATIONAL PLAN**

### **8.1 Overall Study Design and Plan**

The purpose of this equivalence study is to compare the immunogenicity, safety, and efficacy of Gan & Lee Insulin Glargine Injection with that of the reference medicinal product, Lantus®, in adults with type 2 diabetes mellitus.

At the screening visit, subjects will sign the informed consent form (ICF), they will be screened for eligibility, and the following information will be collected: adverse events, medical history (including diabetes mellitus and thyroid disease history), prior and concomitant medications, vital signs, height, body weight, and body mass index (BMI). The following procedures will be performed: 12-lead electrocardiogram (ECG), physical examination, and blood collection for fasting blood glucose (FBG) test, HbA1c, AIA, routine hematology and chemistry testing (complete blood count, metabolic chemistry panel with serum lipids, thyroid-stimulating hormone [TSH] and free thyroxine [T4]). A urinalysis, and for women of childbearing potential, a urine pregnancy test will be performed. At this visit, the subject will be issued a glucometer, test strips, and other supplies, and the Investigator or designee will provide instruction and conduct training on how to use the glucometer for prospective glucose monitoring to document hypoglycemic episodes in a prospective manner. Subjects will be allowed to keep the glucometer after the study, per local ethical and legal guidelines and regulations. Subjects will also receive a Hypoglycemic Events Record in which they will record information about any hypoglycemic events that occur during their participation in the study.

During the 2 weeks between screening and randomization, subjects already on basal insulin will have their insulin dosing optimized according to [Table 3](#) in [Section 8.5.8](#). They will also have any appropriate adjustments in their other antidiabetes medications (OAM) dosing that may be required because of the optimization of their insulin dosing. Subjects who are insulin-naïve will have their OAM dosing optimized to prepare them for starting basal insulin therapy.

Also, at the screening visit, the subject will have a FreeStyle Libre Pro Flash Glucose Monitoring sensor applied to the back of the upper arm according to the manufacturer's instructions.

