5.2 Randomization

Subjects will be randomly assigned in a 1:1 ratio to Gan & Lee Insulin Glargine Injection or Lantus® treatment. Subject randomization will use a randomly permuted block design with varying block sizes and without stratification.

Registration and randomization will take place using a centralized Interactive Web Response System (IXRS). At registration, the IXRS will assign a unique subject identification number that will be used on all of that subject's eCRFs and serious adverse event (SAE) report forms.

This is an open-label study, however, to avoid the introduction of operational bias into final study results and to increase the interpretability and reliability of the data, certain roles of the Sponsor and study team will be blinded. Details are provided in the Data Blinding and Documentation of Aggregate Data Dissemination Plan (hereafter referred to as the Blinding Plan).

6. Endpoints and Covariates

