A summary of events reported, categorized by maximum National Cancer Institute Common Terminology Criteria for Adverse Events (NCI CTCAE) severity grade as reported in the CRF will also be provided. Subjects with multiple events within a particular SOC or preferred term will be counted under the category of their most severe event within that SOC or preferred term. Sorting will be in descending frequency for SOC and descending frequency for preferred term within SOC in the total column.

Subject incidence of the following TEAEs will be tabulated by preferred term in descending order of frequency in the total column:

- Grade \geq 3 AEs
- Hypoglycemic AEs
- Severe hypoglycemic AEs
- IP-related AEs
- Grade \geq 3 IP-related AEs
- AE leading to discontinuation of IP
- IP-related AE leading to discontinuation of IP
- Injection site reactions

Sponsor: Gan & Lee Pharmaceuticals, USA Corporation
Protocol no: GL-GLAT2-3002

Statistical Analysis Plan
Version Date: 16-Nov-2020

A forest plot of the difference in incidence rates and CIs of TEAEs preferred terms with a $\geq 5\%$ difference in incidence between groups will be summarized. The 90% CIs will be computed using Wald method for risk difference without continuity correction.

Additionally, the hypoglycemia event rate will be compared between treatment groups using a negative binomial regression model (Table 6, Analysis 14). The response variable in the model will be the number of hypoglycemia events. The model will include factors for treatment group and site. In this study, sites were found to use variable procedures in their determination, collection and recording of the number of hypoglycemia episodes for individual subjects. So, to account for this additional variation, SITE is planned to be included as a fixed factor in the negative binomial regression model. This model will allow estimation of the site-adjusted, two-sided, 95% confidence interval of the treatment contrast. If that CI includes zero, we will conclude that this study does not provide sufficient evidence that subjects on this biosimilar have different numbers of hypoglycemic episodes compared to those on the reference analogue. The logarithm (to base e) of the follow-up time will be used as an offset variable in the model to adjust for subjects having different exposure times. The estimated treatment effect and the corresponding 95% confidence interval (CI), as well as the 2-sided p-value will be presented.

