A sample SAS code fragment is provided below for reference:

```
proc genmod data = <data>;
    class trt site;
    model count = trt site / dist = negbin offset = time_log;
    lsmeans trt / ilink diff exp cl;
run;
```

All TEAEs will be listed for subjects in the Safety Analysis Set. A listing of all TEAEs leading to discontinuation of IP will be provided.

All non-treatment-emergent AEs recorded on the CRF will be listed separately for all screened subjects.

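### The hypoglycemia rate model has no baseline hypoglycemia term, although a screening sensor count is already derived for each subject; adding it is a cheap gain in precision, of uncertain and possibly small size.

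*Protocol*

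**What the plan says.** **The model.** SAP 11.8.1 (Table 6, Analysis 14) compares hypoglycemia event rates by negative binomial regression. "The response variable in the model will be the number of hypoglycemia events." "The model will include factors for treatment group and site." "The logarithm (to base e) of the follow-up time will be used as an offset variable in the model." The code fragment agrees: "model count = trt site / dist = negbin offset = time_log". The result is a "site-adjusted, two-sided, 95% confidence interval of the treatment contrast". If that interval includes zero, the SAP concludes that the study gives insufficient evidence of different numbers of episodes. Site is in the model because sites determined, collected and recorded episodes in different ways. SAP 11.1 pools sites with fewer than 8 subjects for this analysis.

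**The baseline data.** Protocol 8.6.2 provides for sensors at three times, one of them before randomization: "At the screening visit and between 8 and 10 days before the visits at Weeks 12 and 26, subjects will attend a brief visit". Exclusion criterion 24 removes people who cannot or will not wear the sensor. SAP 11.7.3.1 defines a sensor event at 3.0 mmol/L or below and counts events on days 2-8 for each subject at each wear, for descriptive summary only. Protocol 8.1 also starts a diary at screening: "Subjects will also receive a Hypoglycemic Events Record in which they will record information about any hypoglycemic events that occur during their participation".

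**The setting.** SAP 5.2: "Subject randomization will use a randomly permuted block design with varying block sizes and without stratification." Protocol 8.4.1 admits both insulin-naive and insulin-treated subjects. Protocol 11.3 names hypoglycemia as the adverse event of special interest. For HbA1c, SAP 11.7.1.1 does adjust for the baseline value of the outcome.

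**The concern.** Subjects probably differ widely in their risk of hypoglycemia, and neither the randomization nor the model takes account of it. A pre-randomization measure of that risk is collected, transferred and derived, then left out of the one model that compares event rates between arms.

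Two things are at stake. If the screening count predicts on-study events, leaving it out makes the interval wider than it needs to be. And if the arms happen to differ at baseline, the estimate is not corrected for that difference. The first matters more than usual here, because a wide interval that covers zero leads to the reassuring statement. Imprecision is therefore not neutral.

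**Working it through.** **1. Is there a planned figure to reproduce?** Not for this comparison. Neither document gives a hypoglycemia rate, dispersion, standard error or power. The only power basis is for the primary immunogenicity test (Protocol 12.2: 275 per arm, rate 30%, margin 12%, about 85%). It reproduces: SE = sqrt(2 × 0.30 × 0.70 / 275) = 0.0391, and power = 2Φ(0.12/0.0391 − 1.645) − 1 = 84.6%. This says nothing about hypoglycemia, so every figure below rests on assumptions.

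**2. Direction.** With n = 275 per arm, mean μ events per subject and dispersion k,

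Var(log RR) ≈ (2/275)(1/μ + k).

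If a baseline covariate explains a share R² of the dispersion, this becomes (2/275)(1/μ + k(1 − R²)). With a log link the rate ratio is collapsible, so adding the term does not change what is estimated.

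Example, μ = 3 and k = 2: SE = sqrt(0.00727 × 2.333) = 0.130. At R² = 0.1 it is sqrt(0.00727 × 2.133) = 0.125, a 4.4% reduction. At R² = 0.3 it is sqrt(0.00727 × 1.733) = 0.112, a 13.8% reduction.

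Over μ = 0.5 to 12 and k = 1 to 4:

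| R² | Reduction in SE |
|---|---|
| 0.1 | 1.7-5.0% |
| 0.3 | 5.1-16.0% |
| 0.5 | 8.7-28.6% |

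**3. What a seven-day sensor count can deliver.** A short count is a noisy measure, so R² is lower than the underlying correlation suggests. Simulation assumptions: 275 per arm; 40 sites as fixed effects; log-normal subject risk with SD 1.1; mean on-study events 1, 3 or 6; mean screening events 0.5 or 1.5; equal follow-up; no missing sensor data; 200 runs per scenario. The count entered as log(1 + count) plus an indicator of any event.

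| Correlation of screening and on-study log-risk | Reduction in model SE | Reduction in spread of estimates over runs |
|---|---|---|
| 0 | 0.1-0.7% | −1.6 to 0.8% |
| 0.3 | 0.6-2.1% | −0.5 to 2.1% |
| 0.6 | 3.2-9.4% | 3.2 to 11.0% |

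The last column carries more simulation noise at 200 runs.

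**4. Upper end.** A second set of assumptions used 275 per arm, mean 2 events, gamma subject risk with dispersion 1.5 or 2.5, log-normal noise (SD 0.7) on the screening count only, mean screening events 0.3 or 1.0, and no site effects. Robust SEs fell from 0.120 to 0.115 (4%), 0.120 to 0.109 (9%) and 0.146 to 0.131 (10%). The variance of log gamma risk is 3.06 at dispersion 1.5 and 7.28 at 2.5, so the implied log-risk correlation is sqrt(3.06/(3.06 + 0.49)) = 0.93 or sqrt(7.28/(7.28 + 0.49)) = 0.97. These gains are a best case.

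**5. Chance imbalance.** The 95% range of the difference in arm means of a baseline variable is ±1.96 × sqrt(2/275) = ±0.167 SD. With log-risk SD 1.1, the unadjusted log rate ratio moves by up to 0.3 × 1.1 × 0.167 = 0.055 at correlation 0.3 (ratio 1.06), or 0.6 × 1.1 × 0.167 = 0.110 at 0.6 (ratio 1.12). A noisy count would remove only part of this.

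**The case against.** The strongest reply is that nothing here is wrong. The model is valid under randomization, and its interval already allows for chance imbalance. That stands. A reader might infer that unadjusted imbalance biases the comparison. It does not on average; the loss is conditional on the imbalance that occurs.

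The second reply is that the screening count may predict poorly. This also largely stands. During the screening wear, basal-insulin users are having doses optimized, and insulin-naive subjects have not started the study insulin (Protocol 8.5.8). A sensor count at or below 3.0 mmol/L is also a different quantity from reported events. High correlations are therefore hard to assume, and a reader should not take the 10% figure as typical. For the naive/treated mix, prior insulin use would be the more direct covariate; it was not evaluated here.

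Third, a reader might infer that this is the trial's main safety comparison, or that the SAP will declare no difference. The documents support neither. Safety analyses are not ranked, Analysis 14 is one of 17 entries in Table 6, and the stated conclusion is only that evidence of a difference is insufficient.

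Finally, usable data for every subject cannot be assumed. Exclusion 24 concerns ability and willingness; SAP Appendix 4 lists failure to apply the sensor and repeated failure to return it as deviations, classed as not important; and no missing rate is given.

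What survives is narrower: the covariate precedes randomization, does not depend on how a site records events, and is already derived.

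**Conclusion.** The omission is confirmed in both the text and the code of SAP 11.8.1. The analysis is valid as written, but it may give up precision and does not account for a chance baseline difference, on an endpoint where a wider interval favours the reassuring reading.

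The size cannot be derived from the documents. Under the stated assumptions the standard error of the log rate ratio falls by about 0-1% at zero correlation, 1-2% at 0.3 and 3-9% at 0.6; about 10% needs near-perfect correlation. The gain may be small. The case for the change rests on low cost and on consistency with the HbA1c model, not on a defect. The evidence does not support also asking for a robust variance: that was not tested with site in the model, and the change does not need it.

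**What to change.** Before database lock, amend Analysis 14 in SAP 11.8.1:

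- Add one pre-specified baseline covariate: log(1 + screening sensor events at or below 3.0 mmol/L on days 2-8, scaled per day of valid data).
- Add an indicator for subjects without usable screening sensor data, and define a valid day. Short wears are possible, because screening can fall anywhere from Day -14 to Day -1.
- Keep treatment, site (pooled as in SAP 11.1) and the follow-up-time offset.
- Report the present model, without the covariate, as a sensitivity analysis.

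The timing matters: SAP section 3 has the blinded team unblinded at lock, and a covariate added after that would look data-driven.

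The cost is a short SAP addition and one derived variable from data already transferred. The downsides are the extra missing-data rule, for a number of subjects that the documents do not give, and a gain that may be small.
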